TITLE: Placebo-controlled, double-blind, randomized study of Aerucin[®] as adjunct therapy to antibiotics in the treatment of *P. aeruginosa* pneumonia.

PROTOCOL NUMBER: AR-105-002

INVESTIGATIONAL PRODUCT: Aerucin[®] (aerubumab, AR-105)

PHASE: 2/3

INDICATION(S): Aerucin[®] is intended for use as adjunct therapy for treatment of ventilator-associated pneumonia (VAP) due to *Pseudomonas aeruginosa* (*P. aeruginosa*) in combination with standard of care (SOC) antibiotic therapy.

OBJECTIVES:

Primary Clinical Efficacy Objective

To assess the efficacy of Aerucin[®], administered as a single dose in addition to standard of care (SOC) antibiotic regimen on Clinical Cure rates (resolution of pneumonia) between SOC alone and SOC with Aerucin[®] at Day 21.

Primary Clinical Safety Objective

To assess the clinical safety and tolerability of Aerucin[®] in the study population.

Secondary Clinical Efficacy Objectives

To assess the effect of Aerucin[®], administered as a single dose in combination with SOC antibiotic regimen as an adjunct therapy of *P. aeruginosa* pneumonia, as compared to standard antibiotic therapy alone, on the following parameters:

1. Clinical Cure rates at Day 28, 14 and 7, using the same criteria as for the primary efficacy objective.
2. Time to Clinical Cure.
3. Mortality and Pneumonia-related mortality post-treatment.
4. Respiratory functional assessment: Time on mechanical ventilation (including if tracheostomy is in place). Time on supplemental oxygenation. Measures of respiratory health such as changes in PaO₂/FiO₂, using arterial blood gases and/or pulse oximetry measurements.
5. Overall clinical status: Changes in sequential organ failure assessment (SOFA) score.
6. Health economics: antibiotic utilization, duration of stay in the intensive care unit (ICU), duration of hospitalization, duration of intubation with ventilation or duration of mechanical ventilation if tracheostomy in place.

Pharmacokinetics:

To assess the PK Profile of Aerucin[®].

Secondary Safety Objectives: To assess the immunogenicity of Aerucin[®].

Microbiological Efficacy Objectives

To assess the effect of Aerucin[®], administered as a single dose in combination with SOC antibiotic regimen as an adjunct therapy of *P. aeruginosa* pneumonia, as compared to standard antibiotic therapy alone, on the following parameters

1. Eradication of index *P. aeruginosa* at Day 21 and 28 post-treatment,
2. Re-infection/new infection defined as a reoccurrence of pneumonia due to *P. aeruginosa* within the 28-day follow-up period,
3. Reduction in bacterial load related to the index *P. aeruginosa*

POPULATION:

Persons of either gender who meet all of the following inclusion criteria and none of the exclusion criteria.

Inclusion Criteria

1. Written Informed Consent given by the patient or, if not possible, by a legally authorized representative and/or an independent physician as authorized by the competent ethics committee (EC) or independent review board (IRB) and local regulations.
2. To be at least 18 years of age.

Taiwan only: To be at least 20 years of age.

South Korea only: To be at least 19 years of age.

3. To be treated in an ICU at the time of enrollment.
4. Endotracheal tube in place (tracheostomy is allowed).
5. The patient is mechanically ventilated.
6. Diagnosis of pneumonia based on the following criteria (a, b, and c, all must be met):
 - a. One definitive chest X-ray diagnostic of pneumonia,
or
A sequence of at least 2 chest X-rays showing the presence of new or progressive infiltrate(s) suggestive of bacterial pneumonia.
 - b. Hypoxemia based on at least one of the following measurements/criteria:
 - i. $\text{PaO}_2/\text{FiO}_2 < 250$ mmHg (at sea level or equivalent for significant elevations above sea level) while intubated and mechanically ventilated, as one or more measures within ≤ 24 hours prior to randomization, or
 - ii. $\text{PaO}_2 < 60$ mmHg (at sea level or equivalent for significant elevations above sea level) while intubated and mechanically ventilated, as one or more measures within ≤ 24 hours prior to randomization, or
 - iii. Respiratory failure necessitating intubation and mechanical ventilation. If tracheostomy is in place, the need for mechanical ventilation.
 - c. At least one of the following signs:

-
- i. Documented fever (e.g., body temperature greater than or equal to 38° Celsius).
 - ii. Hypothermia (e.g., core body temperature less than or equal to 35° Celsius).
 - iii. Total peripheral white blood cell (WBC) count greater than or equal to 10,000 cells/ μ L (or mm^3).
 - iv. Leukopenia with total WBC less than or equal to 4,500 cells/ μ L (mm^3).
 - v. Greater than 15 percent immature neutrophils (bands) noted on peripheral blood smear.
7. Documented pulmonary infection with *P. aeruginosa* obtained by bronchoalveolar lavage (BAL), mini-BAL, protected endotracheal tube aspiration (ETA) (collectively ‘airway specimen’). For the study randomization, *P. aeruginosa* must be identified by one of the three methods below:
- a. An airway specimen culture positive by any method for *P. aeruginosa* of a specimen obtained less than 72 hours prior to randomization. A fresh airway specimen must be obtained prior to treatment initiation for baseline standard microbial culture by the local laboratory (including organism identification, quantitative/semi-quantitative culture and susceptibility testing); the corresponding culture results are NOT required prior to randomization.
- OR
- b. A rapid diagnostic test. In such case, the same sample must ALSO be used for standard microbial culture by the local laboratory (including organism identification, quantitative/semi-quantitative culture and susceptibility testing). The corresponding culture results are NOT required prior to randomization.
- OR
- c. A positive airway specimen culture by any method of *P. aeruginosa* from a specimen obtained at screening (quantitative, semi-quantitative).
8. APACHE II score ≥ 10 and ≤ 35 within 24 hours once subject has consented.

Exclusion Criteria

1. The subject is moribund. Clinical judgment by the investigator that the subject is unlikely to survive the current illness/ICU-admission/treatment period despite delivery of adequate antibiotics for treatment of *P. aeruginosa* pneumonia.
2. Effective antibacterial drug therapy for the index pneumonia administered continuously for 48 hours or more prior to initiation of study treatment. Effective antibiotics would include those typically used to treat *P. aeruginosa*.
3. Plasmapheresis (ongoing or planned) or any procedure that would remove/filter out the monoclonal antibody/study drug.
4. Immunocompromised and at risk of infection by opportunistic pathogens including, but not limited to the following:
 - a. HIV / AIDS who are not stable under medication and/or most recent CD4 < 200.

- b. Expected neutropenia due to chemotherapy.
 - c. Absolute neutrophil count less than 500/ μL (mm^3).
 - d. Heart or lung transplant recipient within the past 6 months.
5. Known hereditary complement deficiency.
 6. Liver dysfunction with a Child Pugh C score (Child Pugh score of A or B are acceptable at discretion of the Principal Investigator [PI]).
 7. Pulmonary disease that precludes evaluation of a therapeutic response (such as lung cancer resulting in bronchial obstruction or on the same side as the pneumonia, active tuberculosis, cystic fibrosis, granulomatous disease, fungal pulmonary infection, lung abscess, pleural empyema or post obstructive pneumonia).
 8. Patient has received intravenous (IV) immunoglobulin therapy within 3 months prior to the Screening Visit.
 9. Any woman of child-bearing potential (WOCBP) who does not have a negative pregnancy test result at Screening using SERUM or URINE testing based on Beta-subunit human chorionic gonadotropin (HCG) standard tests and methods from the local laboratory. Non-pregnant and non-lactating with confirmation via local laboratory testing is required. Women who are post-menopausal as evidenced by the absence of menstruation for at least 1 year are eligible; the date of last menstruation is to be recorded in the study files unless post-menopausal status is obvious due to age.
 10. Any sexually active subject who is unwilling to use acceptable methods of contraception for 120 days after dosing. WOCBP must agree to use to an effective method of birth control (e.g., prescription oral contraceptives, contraceptive injections, contraceptive patch, intrauterine device, barrier methods, abstinence) or male partner sterilization alone for the duration of the study and for at least 120 days after dosing. Males with female partners of reproductive potential must agree to practice abstinence or to use a condom (male) plus an additional barrier method (female partner) of contraception for the duration of the study and for at least 120 days after dosing.
 11. Known lack of treatment compliance from prior studies or ongoing medical care based on medical records and PI's judgment and/or the capacity of the patient to comply with all study requirements.
 12. Any medical, psychological, cognitive, social or legal conditions that would interfere in the ability to give an Informed Consent OR the absence of a legally valid representative of the patient or independent physician allowed and able to give consent on his/her behalf.
 13. Participation as a subject in another interventional study within 30 days prior to the first dose of study treatment, or planned participation in such a study during the study or within 30 days of its completion by the patient. Patients who participate in observational or epidemiological studies are eligible provided this does not interfere with their capacity or the capacity of the study staff to comply with all study requirements.

STUDY DESIGN AND DURATION:

This study is an international, multicenter, prospective, double blind, randomized, placebo-controlled, parallel design protocol. It will be performed at multiple ICUs.

Patients with a documented diagnosis of pneumonia, due to *P. aeruginosa*, and require ICU care, who are intubated (or have a tracheostomy tube in place) and are mechanically ventilated, are eligible for screening.

Patients meeting all other eligibility requirements will be assessed for *P. aeruginosa* pulmonary infection on the basis of culture results (known from recent quantitative/semi-quantitative cultures) or on the basis of rapid diagnostic testing of a fresh airway specimen using methods available at the site (e.g. mass spectrometry, PCR, etc.), or using devices such as CE marked Cepheid's GeneXpert[®] with "Investigational / Research Use Only" (IUO / RUO) PA Cartridge, or BioFire Diagnostics, LLC (a BioMerieux company)'s IUO FilmArray[®] LRTI Panel.

Acceptable airway samples are BAL, mini-BAL, or ETA (ETA sample with < 10 squamous epithelial cells and >25 polymorphonuclear cells per low power field). It is expected that some subjects will have a positive rapid diagnostic test result that will not be confirmed by standard microbial culture (quantitative, or semi-quantitative). These subjects will be followed according to all the procedures described in this protocol but will not accrue toward the target microbiologically evaluable intent to treat population (micro-ITT). Subjects with a positive diagnosis of *P. aeruginosa* pulmonary infection will be randomized to receive either investigational product or matching placebo (more than one pathogen allowed, if *P. aeruginosa* is regarded a key pneumonia causing pathogen). In total, approximately 154 microbiologically evaluable subjects will be randomized 1-1 to be treated with placebo plus SOC or Aerucin[®] (20 mg/kg) plus SOC in this Phase 2/3 study.

The randomization procedure will account for the fact that many study sites will enroll only a few patients. Randomization will account for existence of sub-populations regarding oxygen status at baseline ($\text{PaO}_2/\text{FiO}_2 \leq 200$ or > 200).

Study subjects will receive a single treatment dose (at Day 0) in addition to SOC antibiotic treatment, and then enter a safety, efficacy and PK follow-up study period for a total study duration of 28 days. The selection of SOC antibiotics is made in accordance with local best practices at the discretion of the investigator and should not exceed a duration of 14 days.

The clinical course of pneumonia will be assessed daily by the investigator. Once Clinical Cure has been determined, the clinical status of the subject will be monitored to confirm continuation of Clinical Cure, re-infection (pneumonia due to *P. aeruginosa*), or new infection (pneumonia due to an unknown pathogen or a pathogen other than *P. aeruginosa*). "Clinical Cure" can be declared at any time during the study by the PI provided, that the required criteria are met either based on documented improvements in signs and symptoms, +/- changes documented by chest X-ray (if performed as part of SOC), as interpreted by the investigator.

The assessment of Clinical Cure (resolution of pneumonia) by the site investigator will be used for the primary analysis. An adjudication committee will apply newly defined Clinical Cure criteria post hoc in a secondary analysis. "Clinical Cure" will be assessed for analytical purposes on Day 7, 14, 21 (primary efficacy endpoint) and 28.

Clinical safety assessments will be performed on an ongoing basis while predefined laboratory assessments will be performed at baseline, and thereafter at Day 4, 7, 14, 21, and 28. Test results obtained for medical reasons between these mandatory time points will be assessed for adverse events and documented accordingly.

Secondary efficacy endpoints will be assessed in a similar manner during the 28-day period, when appropriate, daily when possible (e.g., time on mechanical ventilation including if tracheostomy is in place, time on supplemental oxygenation, measures of respiratory health such as changes in PaO₂/FiO₂ using arterial blood gases and/or pulse oximetry measurements), or upon occurrence (e.g., antibiotic utilization, duration of stay in the ICU, duration of hospitalization, duration of intubation with ventilation, or duration of mechanical ventilation if tracheostomy in place).

Microbiological endpoints of eradication and re-infection/new infection will be determined based on quantitative/semi quantitative cultures performed by the local laboratory and testing of isolates performed by a central microbiology laboratory.

Two PK analyses will be performed to assess the PK profile of Aerucin® in the target patient population. The pharmacokinetics of Aerucin® will be assessed using a population PK (compartmental modeling) approach as well as a non-compartmental analysis approach. A PK sub-study (“Full PK”) will be included, wherein more extensive sampling will be performed in a small number of patients (from select sites) who provide consent (i.e., 16 patients to obtain 8 patients on active treatment). In the remaining patients, a sparse sampling strategy will be implemented with only a few samples obtained from each patient at varying time points (“Sparse PK”). A compartmental population PK model will be developed using the PK data collected from the sub-study and the sparse samples. PK parameters will be estimated as well as between-subject or inter-individual variability (IIV) and residual variability (RV). The effects of select factors describing the characteristics of sub-populations of interest (e.g. high or low bacterial load, cause of admission [trauma or non-trauma], and type of pneumonia) on the PK of Aerucin® will be assessed via covariate analysis. In addition to the population PK evaluation, non-compartmental analysis of the PK sub-study data will be performed.

The investigational therapy will be studied as an adjunct to antibiotic therapy as prescribed by the study investigator according to the SOC in his/her institution. The duration and nature of the initial and any subsequent antibiotic therapy related to the baseline pneumonia event and other infections will be recorded. Duration of antibiotic treatment for the index pneumonia should not exceed 14 days.

DOSAGE FORMS AND ROUTE OF ADMINISTRATION:

Aerucin® is provided as a sterile solution for intravenous infusion, in the amount of 4.5 mL in 10 mL vials at a concentration of 27.5 mg/mL.

STUDY ENDPOINTS:

Primary Clinical Efficacy Endpoint

The proportion of patients with Clinical Cure at Day 21 in patients treated with Aerucin[®] versus the placebo group as assessed by the investigator. The investigators' assessment will be the primary analysis of the primary endpoint.

Additionally, newly defined Clinical Cure criteria will be applied post-hoc by an independent adjudication committee:

1. The subject must be alive through the index day visit
2. The patient must have **improved respiratory function** evaluated at the index day, because:
 - The patient is now off the ventilator and extubated
 - or
 - if the patient entered the study with mechanical ventilation due to reasons other than pneumonia and was assessed “*likely ventilated beyond day 28*” at screening, criteria #1 (survival) and #3 (no signs and symptoms of pneumonia) are sufficient to establish Clinical Cure (*presumed not ventilated*)
3. The subject must show **no clinical signs and symptoms of bacterial pneumonia** at the index day, which is determined by
 - Not receiving any antibiotic therapy active against the initial *P. aeruginosa* strain or against persisting pulmonary bacterial infection for 48 hours (antibiotic therapy for documented extra-pulmonary infection permitted)
 - and**
 - Resolution of signs and symptoms of bacterial pneumonia, **as determined by the PI based on their clinical assessment**. Parameters to be considered may include:
 - Fever > 38°C or hypothermia (< 35°C) attributable to the primary bacterial pneumonia
 - Tachypnea or shortness of breath (> 22 respirations/min) if off the ventilator and/or back to baseline respiratory rate
 - Tachycardia (> 100 bpm) or bradycardia (< 60 bpm) and/or back to baseline heart rate
 - Improvement of hypoxemia (ABG or PaO₂/FiO₂ > 200 or pulse oximetry > 90%)
 - If patient still produces sputum - negative *P. aeruginosa* culture from sputum, blood or pleural fluid

Secondary Clinical Efficacy Endpoints

1. Proportion of patients with Clinical Cure at Day 28
2. Proportion of patients with Clinical Cure at Day 14
3. All-cause mortality
4. Pneumonia-related mortality
5. Proportion of patients with Clinical Cure at Day 7
6. Change from baseline in respiratory functional assessment: Time on mechanical ventilation (including if tracheostomy is in place). Time on supplemental oxygenation. Measures of

respiratory health such as changes in PaO₂/FiO₂, using arterial blood gases and/or pulse oximetry measurements.

7. Mean change from baseline in overall clinical status measured by SOFA scores.
8. Health economics: antibiotic utilization, duration of stay in the ICU, duration of hospitalization, duration of intubation with ventilation or duration of mechanical ventilation if tracheostomy is in place.

Microbiological Endpoints

Microbiological outcome of the index *P. aeruginosa* pneumonia based on the data provided by the local microbiology laboratory and central microbiology laboratory.

Eradication of *P. aeruginosa* at Day 21 and 28. Eradication is considered as obtained when a specimen of respiratory secretions is obtained between the visit day and Day 28 and is negative. When no specimen is obtained within this time frame, microbiological outcome will be assessed as “Eradicated” only if the study subject is not receiving any antibiotic active against the initial strain after the study drug administration visit day and displays no signs and symptoms of pneumonia.

Change in bacterial load related to the index *P. aeruginosa* on the basis of quantitative or semi-quantitative cultures by the local microbiological laboratory.

Pharmacokinetic Endpoints

Assessment of the PK parameters during full PK sub-study.

Assessment of the PK parameters during sparse PK sub-study.

Safety Endpoints:

1. Assessment of clinical adverse events
2. Assessment of clinical laboratory safety tests
3. Assessment of immunogenicity to Aerucin®

STATISTICAL ANALYSES:

Continuous data will be summarized by means, standard deviations, median, min, and max. Categorical data will be summarized by frequency and percentages.

The primary endpoint of Clinical Cure rate at Day 21 will be analyzed using a stratified Cochran-Mantel-Haenszel (CMH) test. The CMH test will be stratified by baseline randomization strata. Time to Clinical Cure will be analyzed using a stratified log rank test. Other continuous endpoints will be analyzed using an Analysis of Covariance (ANCOVA), with treatment as a main effect, site, and baseline strata as covariates. Treatment by site interaction will be evaluated separately. Secondary endpoints will be analyzed using a sequential procedure in predefined order. Categorical variables will be analyzed using a stratified CMH test.

The primary comparisons for all endpoints will be between the 20 mg/kg dose group and placebo and will be done at 0.05 level of significance. The details of the planned analyses will be provided in the Statistical Analysis Plan.

Demographics, Baseline Characteristics, and Disposition

Demographics and baseline characteristics will be summarized by treatment group and overall. Disposition will be summarized by treatment group, and various outcomes (completed or discontinued the study, and reasons for discontinuation, etc.).

Safety analysis

Safety evaluations will include treatment emergent adverse events, vital signs, physical exam, and laboratory values. Safety will be summarized by treatment group. All treatment emergent adverse events, and serious adverse events, will be coded using the Medical Dictionary for Regulatory Activities (MedDRA). Relationship to treatment, as well as severity will also be summarized. Changes in vital signs and physical exams will be summarized by group. Changes in laboratory values, as well as shifts (normal-> abnormal) will be summarized by treatment group.

Pharmacokinetic analyses

Two types of pharmacokinetic analyses will be performed to assess the PK hypothesis that the PK profile of Aerucin[®] in the target patient population is similar to the profile observed in healthy human volunteers (HV). The first pharmacokinetic analysis will consist of a population PK (compartmental modeling) approach using the combined concentration data collected in the PK sub-study and the sparse concentration data, pooled with the available PK data from healthy volunteers (Study ARC-11-01). A compartmental population PK model will be developed and the effects of select intrinsic and extrinsic factors, including but not limited to patient status (e.g., HV versus patient with pneumonia), high or low bacterial load, and cause of admission [trauma or non-trauma]) on the PK of Aerucin[®] will be evaluated via covariate analysis. The population PK model will be described by the estimation of mean structural model parameters, the magnitude of IIV in these parameters, and the magnitude of RV.

The second pharmacokinetic analysis to be performed will be a non-compartmental analysis of the extensively sampled concentration-time data collected in the PK sub-study. The pharmacokinetic parameters to be derived from the individual concentration time profiles will include: the maximum observed plasma concentration (C_{max}), the time of occurrence of C_{max} (t_{max}), the area under the plasma concentration time curve from time 0 to Day 28 (AUC_{0-28}), the terminal elimination rate constant (λ_z), and, if data permits, the terminal half-life ($t_{1/2}$). Parameter estimates will be summarized and tabulated by individual and overall. Graphs of plasma concentration versus time profiles will be generated for each subject and graphs of mean \pm SD profiles will be generated to compare patient and HV data.

SAMPLE SIZE DETERMINATION:

The primary efficacy endpoint is the proportion of subjects with Clinical Cure at Day 21.

It is assumed that the proportion of subjects with Clinical Cure will be 65% in the placebo group, and 85% in the 20 mg/kg dose group. With 69 subjects per group, there will be > 90% power for a statistically significant difference at a two-sided 0.05 level of significance. Sample size calculation was performed based on Fisher' s Exact test using binomial enumerations (PASS version 14). Assuming a 10% drop-out rate, approximately 154 subjects (77 per group) will be randomized.

SITES: Approximately 120 sites worldwide.

SPONSOR:

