1.5.2 Risks related to the study design and required procedures

Aerucin® will be administered in addition to standard-of-care antibiotic therapy, as determined by the investigator on the exclusive basis of the medical needs of his/her patient. Therefore, participation in this study does not affect the chances of a positive clinical outcome in any given study subject, also taking into account the favorable safety profile of the investigational product.

Except for blood sampling for PK and anti-drug antibody (ADA), and rapid testing of airway specimens for assessing the presence of *P. aeruginosa*, the procedures that are required for the study are all routine procedures, in nature and frequency, for this type of patients whose clinical status requires hospitalization in an ICU. Therefore, with the exceptions noted earlier, this study does not impose an unreasonable burden on the study subjects.

Blood sampling for PK and ADA has been reduced to the minimum necessary by allowing sparse sampling for the majority of the study subjects, on the one hand, and by limiting the required sample volume to the minimum technically necessary for the assays, thus limiting the related burden as much as possible.

Eligible study subjects will be randomized and treated either on the basis of culture results (known from recent cultures) or on the basis of rapid diagnostic testing of airway specimens using devices such as CE marked Cepheid's GeneXpert® with Investigational / Research Use Only (IUO / RUO) PA Cartridge, BioFire Diagnostics, LLC (a BioMerieux company)'s IUO FilmArray® LRTI Panel (please refer to section 14.3). This approach is necessary to allow the study intervention to be implemented as early as possible in the course of the disease, as early treatment is a known driver of clinical outcomes. It is expected that the results of rapid testing will not be confirmed by standard microbial culture in a small number of subjects for various reasons including the possibility of rapid test false positive, inadequate samples, or sample cultures affected by an ongoing antibiotic treatment. This situation is not expected to occur in more than 5% of the randomized subjects. Considering the safety profile of Aerucin® and of similar fully human anti-infective mAbs, this risk is deemed acceptable in the context of this study protocol.

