9.2 Sample Size and Statement of Power

It is assumed that the proportion of subjects with Clinical Cure will be 65% in the placebo group, and 85% in the 20 mg/kg dose group. With 69 subjects per group, there will be > 90% power for a statistically significant difference at a two-sided 0.05 level of significance. Sample size calculation was performed based on Fisher's Exact test using binomial enumerations (PASS version 14). Assuming a 10% drop-out rate, 154 subjects (77 per group) will be randomized.

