## 6.4. Efficacy Analyses

### 6.4.1. Primary Clinical Efficacy Endpoint

#### 6.4.1.1. Primary Analysis

The primary efficacy endpoint is the **proportion of patients** with clinical cure at Day 21 in patients treated with Aerucin® versus the placebo group as assessed by the investigator. The investigators' assessment will be the primary analysis of the primary endpoint.

The proportion of patients with clinical cure rate at Day 21 will be summarized by randomized treatment based on the micro-ITT Population and will be analyzed using a **stratified Cochran-Mantel-Haenszel (CMH) test** based on baseline randomization strata (stratum 1: VABP or non-VABP, stratum 2: PaO2/FiO2 ≤200 or >200, and stratum 3: Americas, Eastern EU, Western EU and Asia). The **P-value** from the stratified CMH test will be presented. Prior to the unblinding, the assessment of each strata and strata combinations with respect to the sample size and the corresponding number of endpoints if any or some strata need to be combined to be able to process with the analysis or an **alternative method is called for (e.g. Fisher's Exact test).**

For the primary analysis, subjects who dropped out or had missing outcome data will be included in the denominator. Missing data will be imputed using the nearest clinical data available prior to that day, i.e. LOCF approach.

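### 154 is used both as the number randomized and as the number microbiologically evaluable, the 10% inflation covers the wrong loss, and the stated power above 90% fails on the plan's own inputs

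*Protocol*

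**What the plan says.** Three places count 154 as evaluable subjects. The Protocol Synopsis (Study Design and Duration), Protocol 3.1 and SAP 3.1 all say "In total, approximately 154 microbiologically evaluable subjects will be randomized 1-1 to be treated with placebo plus SOC". The same paragraphs say that subjects with a positive rapid test that culture does not confirm are followed in full but do not count toward the micro-ITT target.

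Three other places count 154 as subjects randomized: the Protocol Synopsis (Sample Size Determination), Protocol 9.2 and SAP 4. Protocol 9.2 reads "Assuming a 10% drop-out rate, 154 subjects (77 per group) will be randomized"; the other two add that the figure is approximate. The starting figure is 69 per group: "With 69 subjects per group, there will be > 90% power". The assumed rates are 65% and 85%: "It is assumed that the proportion of subjects with Clinical Cure will be 65% in the placebo group, and 85% in the 20 mg/kg dose". The method is Fisher's exact test by binomial enumeration, two-sided at 0.05.

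On unconfirmed subjects, Protocol 1.5.2 says "This situation is not expected to occur in more than 5% of the randomized subjects".

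SAP 6.4.1.1 runs the primary analysis on the micro-ITT population with a stratified CMH test. It says "subjects who dropped out or had missing outcome data will be included in the denominator", with missing outcomes filled by LOCF.

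**The concern.** An enrolment target has to say what is being counted. Recruiting to 154 randomized and recruiting to 154 evaluable are different targets whenever some randomized subjects fail to enter micro-ITT, and the protocol expects some to fail.

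The inflation step also has the losses the wrong way round. Dividing by 0.9 is the right correction when drop-outs leave the analysis. Here they stay in. The subjects who do leave the primary set are the unconfirmed ones, and the sample-size text makes no allowance for them.

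At stake are a clear target for the sites and for the system that closes enrolment, and a power statement that describes the analysis to be run. Checking the second of these shows that the base calculation at 69 per group is itself wrong.

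**Working it through.** **Inputs.** Cure rates 65% and 85%, two-sided 0.05, 69 per group, Fisher's exact test, 10% drop-out, 154 randomized (Protocol 9.2, SAP 4). Allocation 1:1 (Protocol 5.3). At most 5% unconfirmed (Protocol 1.5.2). Primary set micro-ITT with drop-outs retained (SAP 6.4.1.1).

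**Step 1: where 154 comes from.** 69 / (1 − 0.10) = 76.7, rounded up to 77 per group; 2 × 77 = 154. This reproduces the plan's figure, so 154 was derived as a number randomized.

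**Step 2: the two meanings compared.** The 5% is an upper expectation, so ranges run from 0% to 5% and assume that everyone randomized is treated.

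| Meaning of 154 | Randomized | In micro-ITT |
|---|---|---|
| Randomized | 154 | 154 × 0.95 = 146.3, so 146 to 154 (73 to 77 per arm) |
| Evaluable | 154 / 0.95 = 162.1, so up to 163 (164 for equal arms) | 154 (77 per arm) |

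Drop-outs stay in the denominator, so no further 10% comes off either row. Both rows remain above 69 per arm.

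**Step 3: power at 69 per group, as the plan states it.** Two-sided Fisher power is the sum, over all pairs of cure counts (x, y) with Fisher p ≤ 0.05, of Bin(x; 69, 0.65) × Bin(y; 69, 0.85). The result is 73.3%, against a stated figure above 90%. Other methods at 69 per group do not reach 90% either:

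- pooled z, 78.1%
- pooled z by exact enumeration, 79.0%
- arcsine, 79.0%
- unpooled z, 79.6%
- one-sided Fisher at 0.05, 82.1%
- one-sided pooled z at 0.05, 86.4%

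Fisher's test first reaches 90% at 104 per arm (90.0%; 89.7% at 103). With 69 per group and 65% on placebo, a treated rate of about 89% would be needed (90.7%).

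**Step 4: power at the sizes that will be analysed.** The CMH-type column is an exact enumeration of the unstratified statistic. It approximates the planned stratified test.

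| Per arm | Fisher, 65% v 85% | CMH-type, 65% v 85% |
|---|---|---|
| 73 | 75.4% | 80.8% |
| 77 | 78.3% | 83.1% |

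The effect of the two meanings of 154 is 78.3 − 75.4 = 2.9 points by Fisher and 83.1 − 80.8 = 2.3 points for the CMH-type test.

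**Step 5: worst-case bound for retained drop-outs.** If 10% drop out and every one counts as not cured, the rates become 0.9 × 65% = 58.5% and 0.9 × 85% = 76.5%. Power is then 58.3% (73 per arm) to 60.9% (77) by Fisher, and 64.7% to 67.1% for the CMH-type test. Dividing n by 0.9 does not correct for this, because the loss is in the rates and not in the count.

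**The case against.** The best defence is that the design sections already give a workable accrual rule: recruit until 154 are evaluable, and do not count unconfirmed subjects. On that reading the sample-size sections are merely incomplete, most of the statements say approximately, and 146 against 154 is a small difference. Much of this stands. The target is not wholly undefined, and the ambiguity costs only 2 to 3 points of power. What does not stand is that the text settles it. The derivation in Protocol 9.2 and SAP 4 yields a number randomized, and a rounding word does not say which quantity is counted.

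The micro-ITT definition (Protocol 9.1.3, SAP 6.2.3) requires microbiological documentation without naming culture, and SAP 6.4.4 lists a rapid-test-only subgroup within micro-ITT. One could argue that unconfirmed subjects therefore stay in. The design paragraphs exclude them expressly, so this is a second wording gap and does not resolve the first.

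Three stronger readings are tempting, and the documents do not support them:

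- **That the ambiguity and the drop-out rule explain the gap to 90%.** They do not. The gap is present at 69 per group before any loss.
- **That the analysis set falls to 66 per arm (154 × 0.95 × 0.9 / 2 = 65.8), below the planned 69.** This removes drop-outs whom SAP 6.4.1.1 retains.
- **That power is about 60%.** This needs every drop-out to count as a failure. The SAP uses LOCF, which can carry a cure forward, and subjects who stop assessments are telephoned to ascertain Clinical Cure (Protocol Table 6-1 footnote 15 and 8.8). The figure is an extreme bound.

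**Conclusion.** The point holds, in two parts of different size.

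The inconsistency over 154 and the misdirected 10% allowance are real but modest. They leave 73 to 77 per arm in the primary analysis, above the planned 69, and move power by about 3 points. This rests on the protocol's ceiling of 5% unconfirmed, on the design paragraphs' exclusion of those subjects, and on all randomized subjects being treated.

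The power statement is the larger error and has a separate cause. On the plan's own rates, test and significance level, 69 per group gives 73.3%. No method tried reaches 90%. Correcting only the wording of 154 would leave that error in place. The CMH-type figures are approximate because they ignore stratification.

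**What to change.** 1. Use one definition of 154 in all six places (Protocol Synopsis twice, Protocol 3.1 and 9.2, SAP 3.1 and 4). If it means evaluable, state that up to 163 will be randomized at 5% unconfirmed (164 for equal arms). If it means randomized, drop the microbiologically evaluable qualifier and state that 146 to 154 are expected in micro-ITT.
2. Replace the 10% drop-out allowance with one for unconfirmed subjects, and say in Protocol 9.1.3 and SAP 6.2.3 whether micro-ITT requires culture confirmation.
3. Replace the claim of more than 90% power with the power at 73 to 77 per arm: about 75–78% by Fisher, or about 81–83% for an unstratified CMH-type test, labelled as an approximation to the planned stratified CMH. Add, as a worst-case bound only, about 58–61% (Fisher) or 65–67% (CMH-type) if 10% drop out and all count as not cured.

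The cost is a text amendment and a less favourable stated power. If 154 means evaluable, it also means randomizing 163 − 154 = 9 or 164 − 154 = 10 more subjects than Protocol 9.2 states. Keeping a 90% claim would instead need 104 per arm in the analysis, which is a decision on trial size and not a wording change.
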